Inclusion criteria	
 ● Age between 18 and 80 years ● Endoscopic biopsy and CT confirmed locally advanced gastric adenocarcinoma, requiring D2 radical gastrectomy. ● Preoperative examination showed no absolute contraindication and no distant metastasis ● Performance status of 0 or 1 on ECOG scale ● ASA class I, II, or III ● Written informed consent

Exclusion criteria
	
 ● Enlarged or bulky regional lymph node (diameter over 3cm) supported by preoperative imaging including those surrounding important vessels ● Emergency surgery due to complication (bleeding, obstruction or perforation) caused by gastric cancer ● Previous upper abdominal surgery (except laparoscopic cholecystectomy) ● Previous neoadjuvant chemotherapy or radiotherapy ● Unstable myocardial infarction, angina, or cerebrovascular accident within the past 6 months ● FEV1 < 50% of predicted values ● Other malignant diseases ● Severe mental disorder ● Women during breast-feeding or pregnancy

Withdraw criteria
	
 ● Patients intraoperatively/postoperatively confirmed as T4b ● M1 tumor confirmed intraoperatively or postoperatively: distant metastasis only found by intraoperative exploration or postoperative pathological biopsy or a positive postoperative peritoneal lavage cytology examination ● Requirement of simultaneous surgery for other diseases ● Patients intraoperatively confirmed as unable to complete D2 lymph node dissection/R0 resection due to tumor: unable to complete R0 resection due to regional lymph node integration into a mass or surrounded with important blood vessels, which cannot be resected ● Sudden severe complications during the perioperative period (intolerable surgery or anesthesia), which renders it unsuitable or unfeasible to implement the study treatment protocol as scheduled ● Patients who voluntarily quit or discontinue treatment for personal reasons at any stage after inclusion in this study ● Treatment implemented is proven to violate study protocol

Outcome Measures	
Primary Outcome Measures :
 
 ● Overall postoperative morbidity rates 
Secondary Outcome Measures :
 
 ● Intraoperative morbidity rate ● Operative time ● Estimated blood loss ● Number of harvested and metastatic lymph nodes ● the lengths of incision, proximal and distal margins ● Time to first flatus ● Time to first liquid diet ● Postoperative hospital stay ● Total cost
Statistical considerations	
All data analyses will be performed using SPSS statistical software, version 23.0 (SPSS Inc), and the R software environment (R Foundation for Statistical Computing).
 
All data analyses will be conducted on a per-protocol (PP) basis. This study does not fill in missing values. Normally distributed continuous variables will be presented as mean and standard deviation and compared using the t-test if normally distributed, or as median and interquartile range and compared using the Wilcoxon rank-sum test if non-normally distributed; while categorical data will be presented as number and percentages and compared using the Pearson χ^2 test or the Fisher exact test, as appropriate. Sensitivity analysis is used for extreme outlier data. The confidence interval of the parameters is estimated with a 95% confidence interval. The central effect analysis and subgroup analysis are conducted according to the specific situation. All the statistical tests were tested by two sides. A p-value <0.05 is considered statistically significant.

1. Research background

Gastric cancer is a common malignant tumor, and its incidence and mortality are second only to lung cancer. According to estimates by National Cancer Registry of China, there were about 4.29 million new cancer patients and 2.81 million cancer deaths in China in 2015, of which 679,000 new gastric cancer patients and 498,000 gastric cancer deaths were reported^[1]. About 90% of patients in China have advanced gastric cancer at the time of diagnosis. According to statistics, 65% of patients with advanced gastric cancer who have a T stage reaching T3 or T4, and as many as 85% of patients with lymph node metastases occur. Without surgical intervention, the median survival time for advanced gastric cancer is only 5.4 months^[2]. Although many advances have been made in treatment, radical surgery is still the main treatment method for the gastric. In recent years, with changes in dietary habits and other factors, the incidence of proximal gastric cancer and esophagogastric junction carcinoma has gradually increased^[3, 4]. According to UICC, AJCC, JGCA and the consensus and treatment guidelines of Chinese experts, total gastrectomy with D2 lymphadenectomy has become the standard operation for upper gastric cancer and esophagogastric junction carcinoma^[5].

Since Kitano first reported the feasibility and safety of laparoscopic radical gastrectomy, laparoscopic radical gastrectomy has been widely carried out. At present, the multi-center prospective randomized controlled study with large-sample has confirmed that early gastric cancer of laparoscopic radical gastrectomy is safe and feasible. It can achieve the effect of radical tumor resection. The long-term follow-up results show that its clinical efficacy is comparable to that of traditional open surgery, and it has significant minimally invasive advantages. Laparoscopic radical gastrectomy for early gastric cancer has become a recommended treatment guideline^[5]. A multi-center prospective study on distal subtotal gastrectomy for advanced gastric cancer shows that laparoscopic D2 radical distal gastrectomy is safe and feasible^[6, 7]. The current research on laparoscopic D2 radical total gastrectomy shows that laparoscopic D2 radical total gastrectomy is safe and feasible, and the long-term effect is comparable to that of laparotomy. Haverkamp et al. ^[8] meta-analysis that included 314 cases of laparoscopy

and 384 cases of open total gastrectomy showed that although laparoscopy had longer operation time, it could significantly reduce intraoperative blood loss and postoperative complication rate and significantly shorten the length of hospital stay. Etoh et al.^[9] conducted a propensity matching analysis of 2494 cases of laparoscopic and open total gastrectomy patients who were registered online in Japan during 2014-2015, and found that there was no statistical difference in surgical complications, including anastomotic fistula and pancreatic fistula, and there was no difference in early postoperative mortality, reoperation rate and readmission rate between the two groups. However, the laparoscopic group had significantly less intraoperative bleeding, more lymph node dissection, and shorter postoperative hospital stay. Hu Jiankun et al. ^[10] retrospectively analyzed 69 patients and 268 patients who underwent laparoscopic and open D2 radical total gastrectomy from 2006 to 2015, respectively. There were no significant differences between the two groups in terms of total lymph node dissection, blood loss, postoperative hospitalization days, and early postoperative complications, and there were no significant differences in 3-year and 5-year postoperative survival rates between the two groups. We analyzed retrospectively 234 patients with D2 radical total gastrectomy during 2004-2010 with PSM, the number of the lymph node and length of margins in the two groups of patients and there were no significant differences, in terms of intraoperative blood loss, postoperative hospitalization days and postoperative pain, laparoscopic group were significantly better than the open group, The incidence of early postoperative complications was also lower than that of open surgery, and the overall five-year survival rate of the two groups was similar^[11].

However, traditional laparoscopic surgery has some limitations, such as limited mobility of laparoscopic instruments, limited field of view, and the two-dimensional plane, lack of three-dimensionality. Due to the complex anatomical structure of the surrounding gastric vessels and the close proximity of blood vessels, it is easy to cause intraoperative bleeding during the lymph node dissection. Moreover, the operation time is long and the learning curve is also long. Especially for patients with obesity, large anteroposterior diameter, and small rib arch angle, the difficulty will be greater, because the deep and narrow abdominal space will seriously affect the laparoscopic surgery.

In 2000, robotic-assisted surgery began to be used in clinical practice. Due to the 3D high-definition images, the elimination of tremor and the flexibility of operation, robotic-assisted surgery has gradually become a frontier and research hotspot in the field of minimally invasive surgery^[12]. In 2003, Hashizume was the first to report the robotic-assisted radical gastrectomy. Since then, many studies and meta-analyses have confirmed that robot-assisted radical gastrectomy can achieve the same short-term and long-term clinical efficacy as laparoscopy^[13-15]. However, at present, most studies on robotic-assisted gastric surgery are on distal gastric cancer, and there are few reports comparing robotic and laparoscopic total gastrectomy. Yoon et al.^[16] retrospectively analyzed 36 patients and 65 patients who underwent robotic and laparoscopic total gastrectomy from 2009 to 2011. There are no significant differences between the two groups in terms of intraoperative blood loss, postoperative hospitalization days, postoperative complications, and the total number of lymph node dissection. However, the study has a certain limitation. These lymph node dissection method are not completely D2 radical resection. Meanwhile, the proportion of patients with early gastric cancer reached 70%. Son et al.^[17] retrospectively analyzed 51 patients and 58 patients who underwent total gastrectomy with robotic and laparoscopic splene-preserving D2 during 2003-2010. The operative time of robotic-assisted surgery group was longer than that of the laparoscopic group, and there were no significant differences between the two groups in intraoperative blood loss, postoperative hospital stay, postoperative first flatus and intake time, postoperative complications, and the total number of lymph node dissection, but more lymph node dissection was performed by the robot at 10 and 11p than by the laparoscope (3.6vs1.9;P =0.014). Meanwhile, there was no significant difference in the 5-year overall survival rate and disease-free survival rate between the two groups, but 70% of the cases were early gastric cancer. The above-mentioned literatures suggests that robotic versus laparoscopic total gastrectomy is safe and feasible, but the number of reported cases is small, and most of them are patients with early gastric cancer. In China, 90% of patients are diagnosed with advanced gastric cancer, and total gastrectomy for advanced gastric cancer is more difficult and has a wider range of lymph node dissection. Therefore, it is more necessary

to conduct clinical research on robotic-assisted radical gastrectomy with D2 lymphadenectomy for locally advanced gastric cancer. At present, there is no prospective study report on the treatment of locally advanced gastric cancer with robot and laparoscopic D2 lymph node dissection.

Our center reported the first robotic-assisted gastrectomy in China in 2010, and has completed more than 600 cases of robotic-assisted gastrectomy. At present, there is a lack of prospective research literature reports on robot and laparoscopic radical total gastrectomy combined with D2 lymphadenectomy in the treatment of locally advanced gastric cancer, and the safety and effectiveness of robotic and laparoscopic radical total gastrectomy with D2 lymphadenectomy for locally advanced gastric cancer are still unclear. This study intends to conduct the first international prospective study of robot and laparoscopic radical total gastrectomy with D2 lymphadenectomy for the treatment of locally advanced gastric cancer, and to provide evidence-based medicine for the widespread development of robot-assisted total gastrectomy for locally advanced gastric cancer.

2. Objective

The purpose of the prospective trial is to investigate the safety and feasibility between Robotic and laparoscopic radical total gastrectomy with D2 lymphadenectomy for locally advanced gastric cancer.

3. Research design

prospective, single-center, non-randomized, controlled, non-blind, and non-inferiority observation trial

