9.1 Case selection

9.1.1 Selection assessment items

Clinical examination data of patients conducted from hospital admission to enrollment into this study (time period is usually 2 weeks) will be considered baseline data, and must include:

- (1) Systemic status: ECOG score, height, weight, BMI, ASA score;
- (2) Peripheral venous blood: Hb、RBC、WBC、LYM、NEU、NEU%、PLT、MONO
- (3) Blood biochemistry: albumin, prealbumin, total bilirubin, indirect bilirubin, direct bilirubin, AST, ALT, creatinine, urea nitrogen, Total cholesterol, triglycerides, fasting glucose, potassium, sodium, chlorine, calcium
- (4) Serum tumor markers: CEA、CA19-9、CA72-4、CA12-5、AFP
- (5) Full abdominal (slice thickness of 10mm or less, in case of allergy to the contrast agent, CT horizontal scanning is allowed only)
- (6) Upper gastrointestinal endoscopic ultrasonography (EUS) and biopsy, if no EUS, select ordinary upper gastrointestinal endoscopy and biopsy instead
- (7) Chest X-ray (AP and lateral views): cardiopulmonary conditions(Chest CT replacement is permitted)
- (8) Resting 12-lead ECG

(9) Respiratory function tests: FEV1, FVC

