9.2 Preoperative management

- In case of any deterioration of the clinical conditions from the selection time to the expected day of surgery, whether to undergo an elective surgery as planned should be decided in accordance with the judgment of the doctor in charge; if an emergency surgery is required, the case should be withdrawn from PP set according to Withdrawal Criteria;
- For patients with nutritional risks, preoperative enteral/parenteral nutritional support is allowed.
- For elderly, smokers, high-risk patients with diabetes, obesity, and chronic cardiovascular/cerebrovascular or thromboembolic history, among others, perioperative low-molecular-weight heparin prophylaxis, lower-limb antithrombotic massage, active lower limb massage, training in respiratory function, and other preventive measures are recommended. For other potentially high-risk complications not specified in this study protocol, the doctor in charge can decide on the most appropriate approach according to clinical practice and should record it in the CRF.
- For the operative approach of the surgeries in this study should be selected by the doctor in charge according to his/her experience and the specific intraoperative circumstances.
- Preoperative fasting and water deprivation and other before-anesthesia requirements on patients should follow the conventional anesthesia program, which is not specified in this study.
- For prophylactic antibiotics, the first intravenous infusion should begin 30 minutes before surgery. It is recommended to select a second-generation cephalosporin (there are no provisions on specific brands in this study); the preparation, concentration, and infusion rate should comply with routine practice; and prophylaxis should not exceed postoperative 24 hours (special case can be extended to 48 hours) at a frequency of one infusion every 12 hours. If a patient is allergic to

cephalosporins (including the history of allergy or allergy after cephalosporin administration), other types of antibiotics are allowed according to the specific clinical situation and when used over the same period mentioned.

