9.3.1.7 Regulations Regarding Digestive Tract Reconstruction

The digestive tract reconstruction method is determined by the surgeon according to his/her own experience and the specific intraoperative situation. If instrumental anastomosis is used, the surgeon determines whether manual reinforced stitching of the anastomotic stoma is to be performed; the study protocol does not specify.

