10.1 Statistical analysis plan

- Statistical software: we will use SPSS statistical software, version 23.0 (SPSS Inc), and the R software environment (R Foundation for Statistical Computing) to perform statistical analyses.
- Basic principle: The method of differential testing was adopted. The safety population of the study consists of the patients who receive safety evaluation data after the intervention. Descriptive statistics and two-sided tests were conducted for the safety indicators and the incidence of adverse reactions. A p-value <0.05 is considered statistically significant. The confidence interval of the parameters is estimated with a 95% confidence interval.
- Shedding analysis: Total shedding rate of two groups and loss rate due to adverse events will be compared using pearson χ^2 test

- All data analyses will be conducted on a per-protocol (PP) basis.
- Method of outlier determination: the observation value is greater than P75 or less than P25, and the exceed value more than 3 times of the quartile spacing ($=p75-p25$), which will be sentenced to outlier data. During the analysis, the sensitivity analysis is used for outlier data, namely analyzing outcomes including or excluding outlier's data. and if the results are not contradictory, the data is retained; if the contradiction, it depends on the specific circumstances.
- Descriptive statistics: The measurement data gives the mean, the standard deviation and the confidence interval, and the minimum value, the maximum value, the P25, the median and the P75 are given when necessary; matched data also gives the mean and standard deviation of the gap-value, and the median and average rank of the Non-parametric method. The nominal-scale data gives the frequency distribution and the corresponding percentages. The level data gives the frequency distribution and the corresponding percentages, as well as the median and the average rank. Qualitative data give positive rate, positive number, and denominator numbers. The survival data gives the number of events, the number of deletions, the median survival time, and the survival rate.
- Subgroup analysis : Sub-group analysis is to find the factors that may affect prognostic according to the specific circumstances of the data.
- Missing values handling: This study does not fill in missing values

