11.1 Case Report Form (CRF)

11.1.1 CRF Types and Submission Deadline

CRFs used in this study and their submission deadlines are as follows:

- (1) Case Screening: 1-7 days prior to surgery (time frame of three days)
- (2) Enrolling: submitted to the data center at one day prior to surgery
- (3) Surgery: within 1 day after surgery
- (4) Postoperative discharge: within three days after the first discharge
- (5) Follow-up records: 7 days after each specified follow-up time point

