16.2.2 ASA classification

According to the patients' physical status and surgical risk before anesthesia, the American Society of Anesthesiologists (ASA) has categorized patients into 5 levels (I-V levels):

Class I: Well-developed patients with physical health and normal function of various organs, with a perioperative mortality rate of 0.06% -0.08%.

Class II: Patients with mild complications and good functional compensation in addition to surgical diseases, with a perioperative mortality rate of 0.27% -0.40%.

Class III: Patients with severe complications and restricted physical activity but still capable of coping with day-to-day activities, with a perioperative mortality rate of 1.82% -4.30%.

Class IV: Patients with serious complications who have lost the ability to perform day-to-day activities, often have life-threatening conditions, and a perioperative mortality rate of 7.80% -23.0%.

Class V: Moribund patients either receiving surgery or not, have little chance for survival, and a perioperative mortality rate of 9.40% -50.70%.

Generally, Class I/II patients are considered good for anesthesia and surgical tolerance, with a smooth anesthesia process. Class III patients are exposed to some anesthesia risks; therefore, good preparations should be fully made before anesthesia, and effective measures should be taken to prevent potential complications during anesthesia. Class IV patients are exposed to the most risks, even if good preoperative preparations are made, and have a very high perioperative mortality rate. Class V patients are moribund patients and should not undergo an elective surgery.

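### The arms are non-randomised with no stated balancing rule, yet every between-arm comparison the protocol names is unadjusted, so the primary difference is open to confounding by patient selection

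*Protocol*

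**What the plan says.** - **Design.** The Summary and section 3 call the study a "prospective, single-center, non-randomized, controlled, non-blind, and non-inferiority observation trial". Section 3.2 defines the two groups only by the operation.
- **Comparison.** The Summary (Statistical considerations) names the t-test or Wilcoxon rank-sum test for continuous data. For the rest it says "while categorical data will be presented as number and percentages and compared using the Pearson" chi-square test or Fisher's exact test. The primary outcome (section 5.1) is a morbidity rate, so it falls under the second rule.
- **Principle.** Section 10.1 says "The method of differential testing was adopted". It names no regression, weighting, stratification or propensity score. It mentions matched data only as a format for descriptive statistics, and no matching step is defined. Subgroup analysis is a data-driven search for prognostic factors, not an adjustment of the primary comparison.
- **Who gets which operation.** Section 9.2 says the operative approach "should be selected by the doctor in charge according to his/her experience and the specific intraoperative circumstances". It is unclear whether this means group membership or surgical access. Section 9.3.1.7 uses nearly the same wording for reconstruction, which is "determined by the surgeon according to his/her own experience and the specific intraoperative situation".
- **Baseline data.** Section 9.1.1 collects, before surgery, "Systemic status: ECOG score, height, weight, BMI, ASA score", albumin and CT/EUS findings among others. The stated comparison uses none of them.

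**The concern.** Without randomisation or another balancing rule, patients in the two arms may differ in their risk of complications before the first incision. A crude risk difference then estimates the effect of the robot plus the effect of selection. The confidence interval covers sampling error only.

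The protocol itself gives grounds to expect differences in risk:

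- Section 1 says laparoscopy is harder in obese patients and in those with a deep, narrow abdomen, which is a plausible reason to choose the robot selectively.
- ASA classes I to III are all eligible. Annex 16.2.2 puts perioperative mortality at 0.06–0.08% for class I and 1.82–4.30% for class III, a ratio of 1.82/0.08 = 23 to 4.30/0.06 = 72. This is mortality, not the morbidity endpoint, and shows only that eligible patients differ widely in risk.
- Section 1 reports that the same team used propensity-score matching in its own earlier non-randomised comparison of total gastrectomy.

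Eligibility criteria and minimum surgeon experience narrow the case-mix but do not equalise it. If lower-risk patients go to robotic surgery, a false claim of non-inferiority becomes more likely. If harder cases go to it, the bias runs against robotic surgery and the cost is lost power.

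**Working it through.** **The plan's own figure.** Inputs from section 3.3: 15% in both arms, margin 15 points, α = 0.05, power 80%. The normal approximation at one-sided 0.05 gives n = (1.645 + 0.842)² × 2 × 0.15 × 0.85 / 0.15² = 70.07, so 71 per arm. Exact enumeration of the unpooled Z test first reaches 80% power at n = 68 (0.8003), so the stated 68 reproduces. It assumes no confounding. The normal approximation gives 0.789 power at n = 68, or 0.688 at one-sided 0.025, which is what a two-sided 95% interval implies.

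**Illustration (assumed values, not in the protocol).** One binary risk factor with risk ratio RR of 2 or 3, prevalence 20% in one arm and 40% in the other, overall rate 15%, n = 68 per arm, no treatment effect:

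- baseline risk b = 0.15 / (1 + 0.3(RR − 1))
- arm risk = b(1 + prevalence × (RR − 1))
- RR 2: b = 0.1154; arms 0.1154 × 1.2 = 0.1385 and 0.1154 × 1.4 = 0.1615; shift 0.0231
- RR 3: b = 0.09375; arms 0.09375 × 1.4 = 0.1312 and 0.09375 × 1.8 = 0.1687; shift 0.0375

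The chance of declaring non-inferiority is Φ((0.15 − (pR − pL))/se − z), with unpooled se. For false non-inferiority, a true excess of 0.15 is added to the robotic risk. Example, RR 2 with the shift favouring robotic: pR − pL = 0.2885 − 0.1615 = 0.1269 (from unrounded risks), se = 0.0708, so Φ(0.326 − 1.645) = 0.094.

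| Direction of selection | Quantity | No confounding | RR 2 | RR 3 |
|---|---|---|---|---|
| Favours robotic | False non-inferiority, one-sided 0.05 | 0.050 | 0.094 | 0.132 |
| Favours robotic | False non-inferiority, one-sided 0.025 | 0.025 | 0.051 | 0.076 |
| Against robotic | False non-inferiority, one-sided 0.05 | 0.050 | 0.024 | 0.015 |
| Against robotic | Power, one-sided 0.05 | 0.789 | 0.666 | 0.577 |
| Against robotic | Power, one-sided 0.025 | 0.688 | 0.545 | 0.452 |

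**Smaller imbalance.** At 25% versus 35% and RR 1.5 to 2, the shift is 0.7 to 1.2 points, false non-inferiority is 6.0 to 6.9%, and power in the reverse direction is 76 to 73% (one-sided 0.05).

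**Does adjustment help?** A simulation used 4,000 runs per scenario, with the 20%/40% confounder plus five irrelevant covariates, overlap weights, and a standard error allowing for the estimated score. Residual bias was at most 0.2 points, false non-inferiority 5.2 to 5.9% and power 78 to 80% (one-sided 0.05), with an effective sample size of about 91%.

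**Cost in precision.** If weighting loses 10 to 20% of effective sample size and regains no precision, power falls from 0.789 to 0.751 and 0.707. Holding the stated power would need 68/0.9 = 76 to 68/0.8 = 85 evaluable patients per arm. Expected events are 136 × 0.15 = 20.4.

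**The case against.** **The SAP.** Section 10.1 defers further detail to a SAP that was not available, and covariate adjustment is often specified there. This limits the claim to what the protocol names; it cannot be said that no adjustment is planned. But the protocol is not silent. It assigns the primary outcome an unadjusted test, and an adjusted SAP would depart from that.

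**Group formation.** Annex 16.1 is not in the text reviewed, so a rule for entering a group could stand there. The wording in section 9.2 may well concern surgical access, since it refers to circumstances during the operation while enrolment closes the day before. It is therefore not evidence of selection. On either reading, the available text gives no balancing rule.

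**Size.** The 20% versus 40% imbalance is an assumption, and a milder one gives much smaller effects, as shown above. A shift of 2.3 to 3.8 points is also modest beside a 15-point margin. This stands: the error rates are illustrative.

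**The remedy.** The simulation is a best case, because its only confounder is measured. Two factors named in section 1, anteroposterior diameter and rib arch angle, are not in the baseline list of section 9.1.1. Overlap weighting also shifts the target to patients who could plausibly have had either operation. Both limits are real and should be stated. Neither makes the crude comparison the better primary analysis.

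**Conclusion.** The concern holds. Followed as written, the protocol rests a non-inferiority conclusion from non-randomised arms on an unadjusted comparison. Direction and size of the bias cannot be known from the document. Under the assumed imbalance, the shift is 2.3 to 3.8 points, with false non-inferiority of 9 to 13% instead of 5%, or power of 58 to 67% instead of 79%, at one-sided 0.05. Milder imbalance gives less. The defect lies in the stated method and does not depend on these figures. It should be fixed, because it bears on the primary conclusion and the data to reduce it are already collected.

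**What to change.** 1. In the Summary (Statistical considerations) and section 10.1, make the primary estimate a baseline-adjusted risk difference, for example by propensity-score overlap weighting, with a robust or bootstrap confidence interval compared with the 15-point margin. State the population this targets.
2. Name the covariates in advance and keep the list short: age, BMI, ASA, ECOG, clinical T/N category from preoperative CT/EUS, and albumin. With about 20 expected events, weighting suits better than an outcome model with many covariates.
3. Report covariate balance, keep the crude difference as supportive, and say that unmeasured confounding remains.
4. State how the groups are formed, and whether the operative approach in section 9.2 means group membership. Define the analysis group by the approach intended before surgery. The enrolment form can carry it, since section 11.1.1 has "Enrolling: submitted to the data center at one day prior to surgery". Reconcile this with the per-protocol-only rule.

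**Cost.** Wording in these sections, a few hours of programming and at most one added CRF field. The real price is precision: a 10 to 20% loss of effective sample size would take power to 75–71%. The protocol should accept and state that, or resize to 76–85 evaluable per arm.
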